## GASTROINTESTINAL EVENTS

Immune-mediated colitis has been associated with the administration of atezolizumab.

Management guidelines for diarrhea or colitis are provided in [Error! Reference source not found.6](#).

All events of diarrhea or colitis should be thoroughly evaluated for other more common etiologies. For events of significant duration or magnitude or associated with signs of systemic inflammation or acute-phase reactants (e.g., increased C-reactive protein, platelet count, or bandemia): Perform sigmoidoscopy (or colonoscopy, if appropriate) with colonic biopsy, with three to five specimens for standard paraffin block to check for inflammation and lymphocytic infiltrates to confirm colitis diagnosis.

**Table 6. Management Guidelines for Gastrointestinal Events (Diarrhea or Colitis)**

Event	Management
Diarrhea or colitis, Grade 1	
 
Continue atezolizumab.
 
Initiate symptomatic treatment.
 
Endoscopy is recommended if symptoms persist for > 7 days.
 
Monitor closely.
 

Diarrhea or colitis, Grade 2	
 
Withhold atezolizumab for up to 12 weeks after event onset.a
 
Initiate symptomatic treatment.
 
Patient referral to GI specialist is recommended.
 
For recurrent events or events that persist > 5 days, initiate treatment with corticosteroids equivalent to 1-2 mg/kg/day oral prednisone. If the event does not improve within 48 hours after initiating corticosteroids, consider adding an immunosuppressive agent.
 
If event resolves to Grade 1 or better, resume atezolizumab.b
 
If event does not resolve to Grade 1 or better while withholding atezolizumab, permanently discontinue atezolizumab and contact Sponsor-Investigator.c
 

Diarrhea or colitis, Grade 3	
 
Withhold atezolizumab for up to 12 weeks after event onset.a
 
Refer patient to GI specialist for evaluation and confirmatory biopsy.
 
Initiate treatment with corticosteroids equivalent to 1-2 mg/kg/day IV methylprednisolone and convert to 1-2 mg/kg/day oral prednisone or equivalent upon improvement. If the event does not improve within 48 hours after initiating corticosteroids, consider adding an immunosuppressive agent.
 
If event resolves to Grade 1 or better, resume atezolizumab.b
 
If event does not resolve to Grade 1 or better while withholding atezolizumab, permanently discontinue atezolizumab and contact Sponsor-Investigator.c
 
•
 

Grade 4	
 
Permanently discontinue atezolizumab and contact Sponsor-Investigator.c
 
Refer patient to GI specialist for evaluation and confirmation biopsy.
 
Initiate treatment with 1-2 mg/kg/day IV methylprednisolone and convert to 1-2 mg/kg/day oral prednisone or equivalent upon improvement.
 
If event does not improve within 48 hours of initiating corticosteroids, consider adding an immunosuppressive agent.
 
If event resolves to Grade 1 or better, taper corticosteroids over <math>\geq</math> 1 month.
 

GI = gastrointestinal.

a Atezolizumab may be withheld for a longer period of time (i.e., > 12 weeks after event onset) to allow for corticosteroids (if initiated) to be reduced to the equivalent of  $\leq$  10 mg/day oral prednisone. The acceptable length of the extended period of time must be based on an assessment of benefit–risk by the investigator and in alignment with the protocol requirements for the duration of treatment and documented by the investigator.

b If corticosteroids have been initiated, they must be tapered over  $\geq$  1 month to the equivalent of  $\leq$  10 mg/day oral prednisone before atezolizumab can be resumed.

c Resumption of atezolizumab may be considered in patients who are deriving benefit and have fully recovered from the immune-related event. The decision to re-challenge patients with atezolizumab should be based on investigator's assessment of benefit–risk and documented by both the investigator (or an appropriate delegate) and the Sponsor-Investigator.

## ENDOCRINE EVENTS

Management guidelines for endocrine events are provided in Table 7.

Patients with unexplained symptoms such as headache, fatigue, myalgias, impotence, constipation, or mental status changes should be investigated for the presence of thyroid, pituitary, or adrenal endocrinopathies. The patient should be referred to an endocrinologist if an endocrinopathy is suspected. Thyroid-stimulating hormone (TSH) and free triiodothyronine and thyroxine levels should be measured to determine whether thyroid abnormalities are present. Pituitary hormone levels and function tests (e.g., TSH, growth hormone, luteinizing hormone, follicle-stimulating hormone, testosterone, prolactin, adrenocorticotropic hormone [ACTH] levels, and ACTH stimulation test) and magnetic resonance imaging (MRI) of the brain (with detailed pituitary sections) may help to differentiate primary pituitary insufficiency from primary adrenal insufficiency.

**Table 7. Management Guidelines for Endocrine Events**

Event	Management
Grade 1 Hypothyroidism	

Continue atezolizumab.

Initiate treatment with thyroid replacement hormone.

Monitor TSH closely.

Grade 2 Hypothyroidism	

Withhold atezolizumab.

Initiate treatment with thyroid replacement hormone.

Monitor TSH closely.

Consider patient referral to endocrinologist.

Resume atezolizumab when symptoms are controlled and thyroid function is improving.

Grade 3 and 4 Hypothyroidism	

Withhold atezolizumab.

Initiate treatment with thyroid replacement hormone.

Monitor TSH closely.

Refer to an endocrinologist.

Admit patient to the hospital for developing myxedema (bradycardia, hypothermia, and altered mental status).

Resume atezolizumab when symptoms are controlled, and thyroid function is improving.

Permanently discontinue atezolizumab. c

Grade 1 Hyperthyroidism	
TSH <math>\geq</math> 0.1 mU/L and <math><</math> 0.5 mU/L:
 

Continue atezolizumab.

Monitor TSH every 4 weeks.

Consider patient referral to endocrinologist.

 
TSH <math><</math> 0.1 mU/L:
 

Follow guidelines for symptomatic hyperthyroidism.

Consider patient referral to endocrinologist.

Grade 2 hyperthyroidism	
 
Consider withholding atezolizumab.
 
Initiate treatment with anti-thyroid drug such as methimazole or carbimazole as needed.
 
Consider patient referral to endocrinologist.
 
Resume atezolizumab when symptoms are controlled, and thyroid function is improving.
 

Grade 3 and 4 Hyperthyroidism	
 
Withhold atezolizumab.
 
Initiate treatment with anti-thyroid drug such as methimazole or carbimazole as needed.
 
Consider patient referral to endocrinologist.
 
Resume atezolizumab when symptoms are controlled and thyroid function is improving.
 
Permanently discontinue atezolizumab and contact Sponsor-Investigator for life-threatening immune-related hyperthyroidism. c
 

Symptomatic Adrenal Insufficiency, Grades 2-4	
 
Withhold atezolizumab for up to 12 weeks after event onset. a
 
Consider patient referral to endocrinologist.
 
Perform appropriate imaging.
 
Initiate treatment with corticosteroids equivalent to 1-2 mg/kg/day IV methylprednisolone and convert to 1-2 mg/kg/day oral prednisone or equivalent upon improvement.
 
If event resolves to Grade 1 or better and patient is stable on replacement therapy, resume atezolizumab. b
 
If event does not resolve to Grade 1 or better or patient is not stable on replacement therapy while withholding atezolizumab, permanently discontinue atezolizumab and contact Sponsor-Investigator. c
 

Hyperglycemia Grade 1 or 2	
 
Continue atezolizumab.
 
Investigate for diabetes. If patient has Type 1 diabetes, treat as a Grade 3 event. If patient does not have Type 1 diabetes, treat as per institutional guidelines.
 
Monitor for glucose control.
 

Hyperglycemia Grade 3 or 4	
 
Withhold atezolizumab.
 
Initial treatment with insulin.
 
Evaluate for diabetic ketoacidosis and manage as per institutional guidelines.
 
Monitor for glucose control
 
Resume atezolizumab when symptoms resolve and glucose levels are stable.
 
For recurrent Grade 3 or higher events, permanently discontinue atezolizumab and contact Sponsor-Investigator. c
 

Hypophysitis (pan-hypopituitarism), Grade 2 or 3	
 
Withhold atezolizumab for up to 12 weeks after event onset. a
 
Consider patient referral to endocrinologist.
 
Perform brain MRI (pituitary protocol).
 
Initiate treatment with corticosteroids equivalent to 1-2 mg/kg/day IV methylprednisolone and convert to 1-2 mg/kg/day oral prednisone or equivalent upon improvement. a
 
Initiate hormone replacement if clinically indicated.
 
If event resolves to Grade 1 or better, resume atezolizumab. b
 
If event does not resolve to Grade 1 or better while withholding atezolizumab, permanently discontinue atezolizumab and contact Sponsor-Investigator. c
 
For recurrent hypophysitis, treat as Grade 4 event.
 

Hypophysitis (pan-hypopituitarism), Grade 4	
 
Permanently discontinue atezolizumab and contact Sponsor-Investigator. c
 
Refer patient to endocrinologist.
 
Perform brain MRI (pituitary protocol).
 

	
 
Initiate treatment with corticosteroids equivalent to 1-2 mg/kg/day IV methylprednisolone and convert to 1-2 mg/kg/day oral prednisone or equivalent upon improvement.a
 
Initiate hormone replacement if clinically indicated.
 

--	---

MRI = magnetic resonance imaging; TSH = thyroid-stimulating hormone.

a Atezolizumab may be withheld for a longer period of time (i.e., > 12 weeks after event onset) to allow for corticosteroids (if initiated) to be reduced to the equivalent of  $\leq 10$  mg/day oral prednisone. The acceptable length of the extended period of time must be based on an assessment of benefit–risk by the investigator and in alignment with the protocol requirements for the duration of treatment and documented by the investigator.

b If corticosteroids have been initiated, they must be tapered over  $\geq 1$  month to the equivalent of  $\leq 10$  mg/day oral prednisone before atezolizumab can be resumed.

c Resumption of atezolizumab may be considered in patients who are deriving benefit and have fully recovered from the immune-related event. The decision to re-challenge patients with atezolizumab should be based on investigator's assessment of benefit–risk and documented by both the investigator (or an appropriate delegate) and the Sponsor-Investigator.

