## **6.1 Risks Associated with Atezolizumab and Guidelines for Management of Adverse Events Associated with Atezolizumab**

Toxicities associated or possibly associated with atezolizumab treatment should be managed according to standard medical practice. Additional tests, such as autoimmune serology or biopsies, should be used to evaluate for a possible immunogenic etiology.

Although most immune-mediated adverse events observed with atezolizumab have been mild and self-limiting, such events should be recognized early and treated promptly to avoid potential major complications. Discontinuation of atezolizumab may not have an immediate therapeutic effect, and in severe cases, immune-related toxicities may require acute management with topical corticosteroids, systemic corticosteroids, or other immunosuppressive agents.

The following are general recommendations for management of any other adverse events that may occur and are not specifically listed in the following subsections.

- Patients and family caregivers should receive timely and up-to-date information about immunotherapies, their mechanism of action, and the clinical profile of possible immune-related adverse events prior to initiating therapy and throughout treatment and survival follow-up. There should be a high level of suspicion that new symptoms are treatment related.
- In general, atezolizumab therapy should be continued with close monitoring for Grade 1 toxicities, with the exception of some neurologic toxicities.
- Consider holding atezolizumab for most Grade 2 toxicities and resume when symptoms and/or laboratory values resolve to Grade 1 or better. Corticosteroids (initial dose of 0.5-1 mg/kg/day of prednisone or equivalent) may be administered.
- For Grade 2 recurrent or persistent (lasting for more than 5 days) events, treat as a Grade 3 event.
- Hold atezolizumab for Grade 3 toxicities and initiate treatment with high-dose corticosteroids (1-2 mg/kg/day prednisone or equivalent). Corticosteroids should be tapered over 1 month to 10 mg/day oral prednisone or equivalent, before atezolizumab can be resumed. If symptoms do not improve within 48 to 72 hours of high-dose corticosteroid use, other immunosuppressants may be offered for some toxicities.
- In general, Grade 4 toxicities warrant permanent discontinuation of atezolizumab treatment, with the exception of endocrinopathies that are controlled by hormone replacement therapy.

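### Table 7 tells the investigator both to resume and to permanently stop atezolizumab after Grade 3 or 4 hypothyroidism, and gives no condition for stopping

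*Combined protocol and SAP*

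**What the plan says.** The Grade 3 and 4 Hypothyroidism row of Table 7 (section 6.1, Endocrine Events) lists these steps in order: hold atezolizumab, start thyroid hormone, follow TSH, refer to endocrinology, and hospitalize if myxedema is developing. Two bullets on atezolizumab follow.

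- The first reads "Resume atezolizumab when symptoms are controlled and thyroid function is improving". That exact string stands in the Grade 2 hypothyroidism row and the Grade 3 and 4 hyperthyroidism row; the row at issue prints the same words with one comma added.
- The second, which closes the row, reads "Permanently discontinue atezolizumab". It ends with a full stop and a reference to footnote c.

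Footnote c says: "Resumption of atezolizumab may be considered in patients who are deriving benefit and have fully recovered from the immune-related event". It adds that the investigator and the Sponsor-Investigator must both document the decision.

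The general recommendations at the start of section 6.1 say that "Grade 4 toxicities warrant permanent discontinuation of atezolizumab treatment, with the exception of endocrinopathies that are controlled by hormone replacement therapy". Their lead-in limits them to events that the later subsections do not list.

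Section 6 describes its dose delays and modifications as requirements and invites investigators to put questions to the sponsor's team.

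**The concern.** Both bullets cover the same event at the same grades, and neither limits the other. The resume bullet is sound on its own. The defect is that it is paired with an unconditional order to stop.

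Consider a patient with Grade 3 hypothyroidism who is controlled on replacement but has not recovered completely. The resume bullet permits the next infusion. The stop bullet forbids it, and footnote c does not reopen the door, because it asks for complete recovery. One site could re-dose and another could stop for good, each relying on the row.

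The choice matters to the patient. In the Arm C atezolizumab cohort that drug is the only study treatment (Table 3), so stopping it permanently ends protocol therapy. The opposite error is also possible: a site that follows only the resume bullet could re-dose after a very severe event, with nothing in the row marking where dosing must end.

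**Working it through.** The plan gives no figure to reproduce here. The check sets the row beside the rest of Table 7 and the rules around it, and then counts the patients it could reach.

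**1. Rows with both actions.** Table 7 has 11 event rows. Five contain both a resume and a permanent-discontinuation instruction:

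| Row | Stated trigger for permanent discontinuation |
|---|---|
| Hypothyroidism, Grade 3 and 4 | None |
| Hyperthyroidism, Grade 3 and 4 | "for life-threatening immune-related hyperthyroidism" |
| Adrenal insufficiency, Grades 2-4 | No resolution to Grade 1, or "patient is not stable on replacement therapy while withholding atezolizumab, permanently discontinue atezolizumab" |
| Hyperglycemia, Grade 3 or 4 | "For recurrent Grade 3 or higher events, permanently discontinue atezolizumab and contact" the Sponsor-Investigator |
| Hypophysitis, Grade 2 or 3 | No resolution to Grade 1 while the drug is held |

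So 4 of 5 state a trigger, and 5 − 4 = 1 does not.

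**2. Does other text supply the trigger or rank the two bullets?**

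- *Footnote c and the benefit-risk paragraph in section 6.1.* Both concern re-challenge once discontinuation criteria have been met. Both require a patient who is benefiting and has recovered completely. The resume bullet asks only for controlled symptoms and improving thyroid function. These are different tests, so the footnote does not merge the bullets.
- *General recommendations in section 6.1.* The exemption for Grade 4 endocrinopathies controlled on hormone replacement suggests that unconditional stopping is not intended. By its own lead-in, though, the list covers events not dealt with later, and hypothyroidism is dealt with in Table 7.
- *Treatment Interruption in section 6.1.* This stops atezolizumab when it has been held for more than 12 weeks, with exceptions. The row cites neither a 12-week limit nor footnote a, so that rule does not explain the bullet.
- *Section 6.* It invites questions but does not say which bullet prevails.

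**3. Could the text extraction be at fault?** The stop bullet ends cleanly with a full stop and its footnote mark. There is no redaction mark or visible gap.

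**4. Reach.** Inputs from section 1.1: 5 planned Arm C atezolizumab patients, and 8 treated Arm B patients with two grade 5 sepsis events. Section 7.3 defines grade 5 as death.

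- Upper bound = 5 + (8 − 2) = 11, assuming the two deaths were different patients and all six others could still receive atezolizumab.
- Lower bound = 0, because the documents do not say how many patients are still on atezolizumab or have yet to start it.

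The documents give no incidence of Grade 3 or 4 hypothyroidism, so no expected number of affected patients can be calculated.

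**The case against.** The strongest reply is that clinicians will read the bullets in sequence: hold, replace hormone, resume if controlled, otherwise stop. The exemption for endocrinopathies controlled on hormone replacement points the same way. Read strictly, its lead-in would leave that exemption almost nothing to cover, because hypothyroidism, adrenal insufficiency and hypophysitis are all listed in Table 7. The table is titled as guidelines, investigators are told to weigh benefit and risk before each further dose, and the sponsor's team can be asked. This makes divergent practice less likely, and it is probably what was meant. But it remains an inference: the word *otherwise* is not in the row, and four sibling rows state their condition.

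A reader might infer that the bullet is cut short, because it is the only one of Table 7's six permanent-discontinuation rows that does not also direct contact with the Sponsor-Investigator. The documents do not support that. Elsewhere in section 6.1, permanent discontinuation is often ordered without that phrase: Grade 2 pulmonary events (Table 5), confirmed Stevens-Johnson syndrome (Table 12), Grade 2 neuropathy (Table 13), myelitis (Table 14), myositis (Table 18) and suspected HLH or MAS (Table 19).

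A reader might also infer that the missing condition must be a life-threatening event, as in the hyperthyroidism row. That is not established. Table 25 uses life-threatening consequences as a descriptor of Grade 4, so that trigger alone could catch Grade 4 events which the general recommendations would let resume when controlled on replacement. The other rows use non-resolution, instability on replacement or recurrence instead.

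**Conclusion.** The point holds as an internal contradiction in one row of Table 7: resume when controlled, then stop permanently with no condition, and no text ranking the two. It rests on the wording alone and on a count of 4 of 5 comparable rows that do state a trigger.

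It is a minor, patient-level dosing correction, worth making because it concerns safety and the section calls its rules requirements. The reach is 0 to about 11 patients under the assumptions above, and it cannot grow through later enrollment beyond the five-patient atezolizumab cohort, since everyone else now enrolls to abemaciclib alone.

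It would be wrong to infer that the trial's conclusions are at risk. Sample size, power, stopping rules and the efficacy decision rule do not depend on this row. The one analysis it could touch is duration of therapy on atezolizumab in Arm C, an exploratory endpoint (section 13.1.3), and only through an affected patient. Nor do the documents show that any patient has been dosed inconsistently.

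**What to change.** Make the last bullet of the row conditional so that it complements the resume bullet. Suggested wording: *If hypothyroid symptoms remain uncontrolled, or thyroid function fails to improve on replacement while atezolizumab is held, stop atezolizumab permanently and notify the Sponsor-Investigator.* Keep footnote c. This follows the pattern of the adrenal insufficiency row and agrees with the exemption for endocrinopathies controlled on hormone replacement.

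The sponsor should confirm this trigger and state whether a life-threatening event also requires permanent discontinuation, including when it later comes under control on replacement.

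The cost is one sponsor query and one line of protocol text. Design, sample size and analysis stay as they are.

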## OCULAR EVENTS

An ophthalmologist should evaluate visual complaints (e.g., uveitis, retinal events).

Management guidelines for ocular events are provided in [Error! Reference source not found.](#)

**Table 8. Management Guidelines for Ocular Events**

Event	Management
Ocular Event, Grade 1	
 
Continue atezolizumab.
 
Patient referral to ophthalmologist is strongly recommended.
 
Initiate treatment with topical corticosteroid eye drops and topical immunosuppressive therapy.
 
If symptoms persist, treat as a Grade 2 event.
 

Ocular Event, Grade 2	
 
Withhold atezolizumab for up to 12 weeks after event onset.a
 
Patient referral to ophthalmologist is strongly recommended.
 
Initiate treatment with topical corticosteroid eye drops and topical immunosuppressive therapy.
 
If event resolves to Grade 1 or better, resume atezolizumab.b
 
If event does not resolve to Grade 1 or better while withholding atezolizumab, permanently discontinue atezolizumab and contact Sponsor-Investigator.c
 

Ocular Event, Grade 3 or 4	
 
Permanently discontinue atezolizumab and contact Sponsor-Investigator.c
 
Refer patient to ophthalmologist.
 
Initiate treatment with corticosteroids equivalent to 1-2 mg/kg/day IV oral prednisone.
 
If event resolves to Grade 1 or better, taper corticosteroids over <math>\geq 1</math> month.
 

a Atezolizumab may be withheld for a longer period of time (i.e., > 12 weeks after event onset) to allow for corticosteroids (if initiated) to be reduced to the equivalent of  $\leq 10$  mg/day oral prednisone. The acceptable length of the extended period of time must be based on an assessment of benefit–risk by the investigator and in alignment with the protocol requirements for the duration of treatment and documented by the investigator.

b If corticosteroids have been initiated, they must be tapered over  $\geq 1$  month to the equivalent of  $\leq 10$  mg/day oral prednisone before atezolizumab can be resumed.

c Resumption of atezolizumab may be considered in patients who are deriving benefit and have fully recovered from the immune-related event. The decision to re-challenge patients with atezolizumab should be based on investigator's assessment of benefit–risk and documented by both the investigator (or an appropriate delegate) and the Sponsor-Investigator.

## **IMMUNE-MEDIATED CARDIAC EVENTS**

### **IMMUNE-MEDIATED MYOCARDITIS**

Immune-mediated myocarditis has been associated with the administration of atezolizumab. Immune-mediated myocarditis should be suspected in any patient presenting with signs or symptoms suggestive of myocarditis, including, but not limited to, laboratory (e.g., B-type natriuretic peptide) or cardiac imaging abnormalities, dyspnea, chest pain, palpitations, fatigue, decreased exercise tolerance, or syncope. Myocarditis may also be a clinical manifestation of myositis or associated with pericarditis (see section on pericardial disorders below) and should be managed accordingly. Immune-mediated myocarditis needs to be distinguished from myocarditis resulting from infection (commonly viral, e.g., in a patient who reports a recent history of gastrointestinal illness), ischemic events, underlying arrhythmias, exacerbation of preexisting cardiac conditions, or progression of malignancy.

All patients with possible myocarditis should be urgently evaluated by performing cardiac enzyme assessment, an ECG, a chest X-ray, an echocardiogram, and a cardiac MRI as appropriate per institutional guidelines. A cardiologist should be consulted. An endomyocardial biopsy may be considered to enable a definitive diagnosis and appropriate treatment, if clinically indicated.

Patients with signs and symptoms of myocarditis, in the absence of an identified alternate etiology, should be treated according to the guidelines in [Error! Reference source not found.9](#).

